ClinicalTrials.gov ID: NCT04535362
Brief Title: Nicotine's Potential Abuse With Menthol
Date: 6.16.2023
Document: Protocol w SAP

1. Principal Investigator: [name]., Ph.D.

2. Co-Investigators While all research staff are trained to provide informed consent, those identified with an asterisk (*) will provide informed consent for this study. All the research staff will have access to the PHI

Co- Investigator: [name].

Nursing Staff: *[name], [name], R.N.,

Research Staff: *[name], BS, and *[name]

3. Title of Project: Impact of Menthol on the Abuse Potential of Nicotine

4. Purpose, hypothesis and key questions:

Specific Aim: To examine if switching from menthol to non-menthol cigarettes will change the dose-effect curves for positive subjective effects and alleviation of smoking urges as a function of nicotine delivery rate in smokers.

Hypothesis #1: Switching to non-menthol cigarettes, compared to smoking menthol cigarettes, will enhance responses to nicotine for both positive subjective effects and alleviation of smoking urges as reflected by a leftward shift in dose-effect curves.

Exploratory Aims:

Exploratory Aim#1: To examine if switching from menthol to non-menthol cigarettes will change the dose-effect curves of nicotine delivery rate for a) reinforcement (assessed with the monetary value of the dose from the Multiple-Choice Procedure, b) heart rate and blood pressure, and c) tobacco withdrawal severity (assessed with self-report symptoms and cognitive performance).

Exploratory Aim#2: To examine the impact of plasma nicotine levels and rate of nicotine metabolism (measured by plasma hydroxy cotinine/cotinine ratio) on the dose-effect curves for the main study outcomes.

Exploratory Aim#3: To examine sex differences for the main study outcomes.

5. Background:

Nicotine control policies to reduce the addictive potential of tobacco products:

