A large body of evidence supports the potential impact of menthol in facilitating the initiation of cigarette smoking (34). However, menthol's effects on nicotine's reinforcing and addictive properties are not well understood. Preclinical studies reported that menthol has inhibitory effects on $\alpha 7$, $\alpha 3\beta 4$ and $\alpha 4\beta 2^*nAChR$ subtypes (35-37), although menthol may also enhance nicotine's reinforcing effect (38). To better understand the potential contribution of menthol to nicotine's addictive effects, we examined if menthol administered by inhalation via an e-cigarette would change the subjective effects of nicotine administered intravenously in menthol and non-menthol preferring smokers (See Preliminary Studies). We found that menthol produces minimal positive subjective effects, alone or in combination with nicotine. However, menthol-preferring smokers, compared to non-menthol preferring smokers, had diminished positive subjective responses to IV nicotine, and had less severe tobacco withdrawal following overnight abstinence. In addition, mentholated cigarette smoking was also associated with a lower nicotine metabolite ratio (NMR), a biomarker for the rate of nicotine metabolism (39, 40). This finding is consistent with previous studies demonstrating an inhibitory effect of menthol on nicotine metabolism (40, 41). A slower rate of nicotine metabolism, as assessed by a lower NMR, is associated with lower urges to smoke and less severe withdrawal symptoms following nicotine deprivation, and reduced positive subjective effects to IV nicotine (42, 43). Thus, the impact of menthol on nicotine's addictive effects may be partly due to menthol's inhibition of nicotine metabolism and this effect seems to be reversible after switching from menthol to non-menthol cigarettes (41). In a carefully conducted study with menthol smokers, switching to non-menthol cigarettes for one week, compared to a menthol-cigarette condition, was associated with an increased rate of nicotine metabolism (41). Together, these findings support the modulatory effects of menthol on the abuse liability and addictive effects of nicotine. Whether menthol-cigarette smoking affects the sensitivity for nicotine delivery rate has not been determined. Similarly, it has not been examined whether switching from menthol to non-menthol cigarettes changes sensitivity to nicotine's effects. This is an important knowledge gap given the widespread use of menthol in both tobacco cigarettes and e-cigarettes. The current study will address these questions by systematically examining the impact of nicotine delivery rate in both menthol and non-menthol smokers and by examining the impact of delivery rate after switching from menthol to non-menthol cigarettes.

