Nicotine administration: Nicotine bitartrate will be obtained from Interchem Corporation, Paramus, NJ, and solutions for IV injection will be prepared by U.S. Specialty Formulations, Bethlehem, PA. On the morning of each test session, weight-adjusted nicotine and saline solutions will be prepared by the West Haven VA research pharmacy. Nicotine and saline will be administered using an infusion pump connected to an IV catheter located in a forearm vein. We have followed these procedures in our previous studies, which were completed without any serious adverse effects attributed to nicotine or other safety concerns. [name] holds an ITP (Investigational Tobacco Product) for IV nicotine administration. A new ITP application has been submitted to the FDA for this project.

In each test session, there will be a total of 3 infusions. Each infusion duration will be 10 minutes long, which will be achieved by infusing saline for the remainder of the time following the 2.5- and 5-minute nicotine infusions. A research nurse, will program 2 infusion pumps to administer nicotine or saline solutions. For the 2.5 and 5 min infusion conditions, participants will first receive nicotine for 2.5 and 5 minutes, followed by saline infusions. For the saline condition, participants will receive saline for 10 minutes. The participants will be blind to the randomization. The order of infusions will be: 1) 5-min or 2.5-min nicotine infusion, 2) saline infusion and 5-min or 2.5-min infusion. This infusion order was chosen to minimize carry over effects between nicotine infusions. Participants will be blind to the order of nicotine infusions.

Justification for the nicotine doses and infusion rates: The total nicotine dose for each test session will be 2 mg/70 kg body weight, a dose within the range of nicotine delivered by smoking 1 or 2 tobacco cigarettes or e-cigarettes (21). For safety reasons, the maximum dose of nicotine for each infusion will be 1 mg. The infusion rates will be 0.096 and 0.048 $\mu\text{g}/\text{kg}/\text{second}$ over 2.5 and 5 minutes, respectively.

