Medical monitoring: Participants will be given a thorough physical examination prior to study entry. For nicotine administration sessions, participants will be attached to a cardiac monitor as well as a blood pressure and heart rate monitoring device. An IV catheter for nicotine delivery will be in place throughout each test session. Participants will be administered nicotine only if the systolic blood pressure is <150 mmHg and heart rate is <90 beats/minute. Participants will be terminated from the study if the blood pressure at any time is >170/110 mm Hg, if the heart rate is >130 beats/min, or if they develop signs and symptoms consistent with nicotine toxicity. We have not encountered any cases of nicotine toxicity in our nicotine infusion studies. These study procedures were developed as part of our Investigational Tobacco Product (ITP) application to the FDA for IV nicotine.

Overview of the study: We propose a placebo-controlled study that will recruit male and female menthol nicotine dependent smokers. Following screening and evaluation as described above, eligible participants will be enrolled in the study which will last about 4 weeks. Eligible, participants will be randomized to menthol or non-menthol smoking condition for 2 weeks (Phase 1) and then will be switched to the alternative condition for another 2 weeks (Phase 2). The smoking condition will be open label. Participants will be provided with free cigarettes in Phases 1 and 2. For the menthol condition, participants will be provided their usual brand of menthol cigarettes and for the non-menthol condition, they will be provided a matched-brand non-menthol cigarette (e.g., Newport Non-Menthol Gold 100s for those who smoke Newport Menthol Gold 100s). In week 2 of each Phase, participants will have a test session. Each session will include 3 infusions in the following order: nicotine (1 mg per 70 kg body weight to a maximum dose of 1 mg) delivered over 2.5 or 5 minutes, saline delivered over 10 minutes, and nicotine (1 mg/ 70kg to a maximum dose of 1 mg) delivered over 2.5 or 5 minutes). For safety reasons, the maximum dose of nicotine for each infusion will be 1 mg. The infusion rates will be 0.096 and 0.048 µg/kg/second over 2.5 and 5 minutes, respectively. Once the participants complete the test session, participants will be crossed over to the alternative treatment. The period between the 2 Phases will not be longer than one week.

Table 1: Study Overview

Procedures	Study Phases	

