Test Session: The schedule of events during the test sessions is shown in Table 2. The sessions will begin around 8 AM, following overnight nicotine abstinence. Before the session begins, participants will have two indwelling catheters placed in antecubital veins, one for administering infusions and one for collecting blood samples. A blood sample will be drawn prior to the first infusion to measure baseline levels of plasma nicotine and menthol glucuronide and for women, additional samples for the measurement of estradiol and progesterone levels will be collected. Baseline measurements will then be collected including heart rate, blood pressure, self-report assessments and cognitive testing. Participants will then receive the assigned infusion over a period of ten minutes. Psychometric assessments and blood sampling will then continue for the next 120 minutes. Participants will be discharged after evaluation by the study physician. Participants will also receive their assigned cigarettes at the end of the session.

Table 2. Schedule of Events: Test Session*

Time point (min)	Measures and Events
Baseline	CO, urine and blood samples, HR/BP, M-NWSC, BQSU, SAFTEE, CPT
0	IV Infusion 1 (nicotine over 2.5 min or 5min) starts
1	HR, DEQ, plasma nicotine
3	HR, DEQ, plasma nicotine
5	HR, DEQ
6	plasma nicotine
8	HR, DEQ
10	IV Infusion 1 ends, HR, DEQ, BQSU,
12	plasma nicotine
13	HR, DEQ,
15	HR, DEQ, plasma nicotine
18	HR, DEQ
20	HR, DEQ, plasma nicotine
25	HR, DEQ,
30	HR/BP, DEQ, BQSU, CPT, M-NWSC, MCP
45	HR, DEQ, BQSU, M-NWSC CPT, plasma nicotine
60	IV Infusion 2 (Saline) starts
61	HR, DEQ, plasma nicotine
63	HR, DEQ, plasma nicotine

65	HR, DEQ
66	plasma nicotine
68	HR, DEQ
70	IV Infusion 2 ends, HR, DEQ, BQSU,
72	plasma nicotine
73	HR, DEQ,
75	HR, DEQ, plasma nicotine
78	HR, DEQ
80	HR, DEQ, plasma nicotine
85	HR, DEQ,
90	HR/BP, DEQ, BQSU, CPT, M-NWSC
105	HR, DEQ, BQSU, M-NWSC CPT, plasma nicotine
120	IV Infusion 3 (nicotine over 2.5 min or 5min) starts
121	HR, DEQ, plasma nicotine
123	HR, DEQ, plasma nicotine
125	HR, DEQ
126	plasma nicotine
128	HR, DEQ
130	IV Infusion 3 ends, HR, DEQ, BQSU,
132	plasma nicotine
133	HR, DEQ,
135	HR, DEQ, plasma nicotine
138	HR, DEQ
140	HR, DEQ, plasma nicotine
145	HR, DEQ,
150	HR/BP, DEQ, BQSU, CPT, M-NWSC
165	HR, DEQ, BQSU, M-NWSC CPT, plasma nicotine
180	End of session, HR/BP, DEQ, plasma nicotine, M-NWSC, BQSU, SAFTEE, MCP
190	Discharge

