repeated measures. Because of the potential skewed distributions of the subjective effects data, transformations will be applied as necessary. We will evaluate the main and interactive effects of cigarette assignment and delivery rate. We anticipate statistically significant main effects of cigarette assignment, nicotine delivery rate and a significant interaction between cigarette assignment and nicotine delivery rate. To better understand the dose effects of nicotine delivery rate and whether they are moderated by cigarette assignment, we will construct specific contrasts among the four doses to test whether there is an indication of significant linear, quadratic, linear on log-scale or sigmoidal dose-response relationships across, or within menthol-preference groups. The possible dose-response curves identified by the specific mean contrasts will be compared by fitting linear and non-linear (as necessary) dose-response models with continuous dose and selecting the best-fitting model by the Akaike's Information Criterion (AIC). To test for an effect of delivery rate on smoking urges, assessed by the BQSU (Factor 1 and 2) scores, we will use similar modeling approach described for subjective effects, but we will also include time as a within-subject factor with outcomes for minute 0, 10, 30, 60 and 120. We anticipate a significant main effect of menthol-preference, nicotine delivery rate and potentially a significant interaction between cigarette assignment and nicotine delivery rate.

Exploratory Aim#1: To explore the dose-effect curves of nicotine delivery rate for a) reinforcement (assessed with the Multiple-Choice Questionnaire), b) heart rate and blood pressure, and c) tobacco withdrawal severity, assessed with self-report symptoms and cognitive performance.

The primary outcome for the analysis of reinforcement will be the crossover point determined by the monetary choice procedure for the four infusion conditions. The crossover point is the monetary value at which a subject chooses money over receiving the infusion for that condition. It is a continuous measure (dollar amount) from -20 to +20 with values > \$0 indicating reinforcement. Tobacco withdrawal severity is measured by the MNWS and CPT taken at 0, 30, 60 and 120 min after the beginning of infusion. The models will be similar to the one described for Specific Aim #1 with time as an additional within-subject factor for heart rate, blood pressure and tobacco withdrawal severity.

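### Specific Aim #1's follow-up contrasts are written for four doses and menthol-preference groups, but the design has three delivery levels in one crossover group, and neither the delivery-rate test nor the leftward shift is defined

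*Combined protocol and SAP*

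**What the plan says.** All references are to the combined protocol and SAP.

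- **Hypothesis** (4. Purpose, hypothesis and key questions). Switching to non-menthol cigarettes will enhance responses to nicotine, "as reflected by a leftward shift in dose-effect curves".
- **Design** (C) Study procedures, Overview of the study). Menthol smokers are randomised to menthol or non-menthol cigarettes and then all switch to the other. "Each session will include 3 infusions in the following order": nicotine over 2.5 or 5 minutes, saline, nicotine over 2.5 or 5 minutes. The nominal rates are 0.096 and 0.048 µg/kg/s, and each nicotine infusion is capped at 1 mg.
- **Saline** (B) Drugs, Nicotine administration). It is treated as a condition in its own right: "For the saline condition, participants will receive saline for 10 minutes". Table 2 puts it second in every session, at minute 60 ("IV Infusion 2 (Saline) starts").
- **Main model** (7) Statistical analysis and sample size estimates, Specific Aim #1). A linear mixed model with cigarette assignment, phase and nicotine delivery condition as within-subject factors. Main effects of assignment and delivery rate, and their interaction, are expected to be significant.
- **Follow-up** (same section). "we will construct specific contrasts among the four doses to test whether there is an indication of significant linear, quadratic, linear on log-scale or sigmoidal" relationships, across or within menthol-preference groups. Linear and, where needed, non-linear models in continuous dose are then compared by AIC. For smoking urges the plan expects a main effect of menthol preference.

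**The concern.** The follow-up describes a different design: four doses instead of three delivery levels, and preference groups instead of one group that crosses over. Two consequences go beyond wording.

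First, delivery rate is the aim's central variable, yet the comparison that isolates it (2.5 versus 5 minutes, same nicotine amount) is never named. If saline is a level of the factor, a significant effect could be reported as a delivery-rate effect when only nicotine versus saline differs. In the same way, a significant interaction could be reported as menthol changing sensitivity to rate.

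Second, Hypothesis #1 is to be judged by a leftward shift, but the statistical section defines no shift or location parameter and no test of one. A larger response after switching could be called a leftward shift although no planned test separates it from an upward shift. Section 6 (Significance) says the results should help set benchmarks for nicotine delivery rates, so both labels matter.

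**Working it through.** **1. The plan's own figures.** The sample-size rationale gives n=30, level 0.025, f=0.6 for cigarette condition and f=0.65 for its interaction with delivery rate. It gives no formula, so I assume a noncentral F with λ = n f².
- f=0.6: λ = 30 × 0.36 = 10.8, df (1, 29), power 81.6%.
- f=0.65, three levels: λ = 30 × 0.4225 = 12.7, df (2, 58), power 81.5%.
- f=0.65, four levels: df (3, 87), power 76.4%.

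The stated figure of over 80% is reproduced with three levels and not with four. Under this assumed convention, that suggests the power statement was built for three.

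**2. Number of levels.** 0.048 × 300 s = 0.096 × 150 s = 14.4 µg/kg, so the two infusions differ in rate and not in nominal amount. With saline there are three levels: 0, 0.048 and 0.096. Above 70 kg the 1 mg cap lowers the rates: at 100 kg, 1000/100/150 = 0.067 and 1000/100/300 = 0.033. These extra values come only from weight differences between people.

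**3. What three levels allow.** Within a cigarette condition there are 2 df for shape. For equally spaced rates the contrasts over (saline, 5 min, 2.5 min) are:
- linear (−1, 0, +1), which is 2.5 minutes versus saline;
- quadratic (+1, −2, +1);
- 2.5 versus 5 minutes (0, −1, +1) = ½ linear + ½ quadratic.

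Neither shape contrast isolates the rate comparison. Log rate is undefined at saline and no offset c is given. With log(rate + c), the saline-to-0.048 step is ln((0.048+c)/c) / ln((0.096+c)/c) of the range: 63% for c=0.048, 74% for c=0.01 and 85% for c=0.001.

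**4. Three-level tests when the two rates do not differ.** Response sizes and SDs are assumptions, because the documents give none. n=30, level 0.025, df (2, 58).
- Main effect, both rates D above saline: λ = 60 × (2/3)D²/SD² = 40 D²/SD². This is divided by 3 if a delivery-condition-within-subject SD equals the residual SD.
- Interaction, assignment changing both nicotine responses by d: λ = 30 × (2/3)d²/(2 SD²) = 10 d²/SD².

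| Residual SD | Main effect, D = 10–15 mm | Same, with delivery-condition SD | Interaction, d = 10–15 mm |
|---|---|---|---|
| 10 mm | about 100% (λ 40–90) | 84–99.7% (λ 13.3–30) | 70–98% (λ 10–22.5) |
| 20 mm | 70–98% (λ 10–22.5) | 24–55% (λ 3.3–7.5) | 17.6–42% (λ 2.5–5.6) |

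In matching simulations the 2.5 versus 5 minute contrast rejected in 2.3–2.8% of trials and its interaction with assignment in 2.4–2.6%, as they should at 0.025.

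**5. Left versus upward shift.** I assumed a maximum of 50 mm, ED50 0.024, 0.048 or 0.096, a 1.5- or 2-fold left shift, the true Hill exponent known, and n=30. The best upward-shift model (common baseline and ED50, separate maxima) was fitted to the true left-shift means. Power is from a 1-df chi-square with λ = 30 × RSS/SD², at 0.025:

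| Hill exponent | SD 10 mm | SD 20 mm |
|---|---|---|
| 1 | 3.8–9.3% | 2.8–4.1% |
| 2 | 11.5–77% | 4.5–23% |
| 3 | 9.4–99.6% | 4.1–58% |

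The range is about 3% to 99.6%, so separation depends on the assumed steepness.

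**6. What a left shift does to the rate comparison.** With baseline 5, maximum 50 and Hill 1, halving ED50 from 0.1 raises the 5- and 2.5-minute responses by 8.3 and 8.4 mm, a change in rate difference of about 0.1 mm. Over the grid in step 5 a left shift moves the 2.5-minus-5-minute difference by −2.2 to +0.2 mm (Hill 1), −7.9 to +1.6 (Hill 2) and −14.7 to +4.3 (Hill 3). It has no predicted direction.

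**The case against.** The case on the other side is substantial, and much of it stands.

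- **The main model fits the design**, and it contains a planned assignment-by-delivery interaction. A reader might infer that the Aim #1 analysis cannot be run. The documents do not support that: the model is estimable, some shape contrasts can be computed, and non-linear fits are planned only where needed.
- **AIC.** A reader might infer that a curved model could never beat a quadratic. That holds for a single curve with three or more mean parameters fitted to the three nominal rates. A joint fit over both cigarette conditions is different: a shared Emax curve with assignment-specific ED50 has 4 mean parameters against 6 for quadratic by assignment, and it can win. But the plan does not specify that model.
- **The interaction.** A reader might infer that a significant interaction from an equal change at both rates is a false positive. It is not. It is a real change in nicotine response, and an equal rise after switching is what Hypothesis #1 predicts. Only calling it changed rate sensitivity would mislead.
- **The main-effect calculation is nearly circular**, since it assumes that nicotine exceeds saline, and the plan does not say that saline is a level of delivery rate. Both points are true. The calculation shows what the label would mean if saline is included, and the silence is itself the gap.
- **Four could mean two rates by two cigarette conditions.** Those are not four points on a dose axis, and each curve still has two active rates.
- **Response sizes are invented.** Yes. They show dependence on assumptions and do not measure a defect in this trial.

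**Conclusion.** The concern holds as a mismatch between the planned follow-up and the design, together with two undefined tests. The text alone establishes three points: there are three delivery levels and one crossover group, against four doses and preference groups; 2.5 versus 5 minutes is not named; and the leftward shift has no parameter or test.

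The size of the labelling risk is conditional. If saline is a level of delivery rate and both rates sit 10–15 mm above it without differing, the three-level effect is significant in 24% to about 100% of trials, depending on residual SD (10 or 20 mm) and delivery-condition variance. The corresponding interaction is significant in 17.6–98%. A shift can be estimated, and can win on AIC, only under a joint shared-curve model that the plan does not specify.

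A reader might also infer that the sample size is wrong. This point does not show that: the f=0.6 and f=0.65 power statements are reproduced with three levels under the assumed convention. The matter should be fixed before analysis, and the fix changes wording only.

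**What to change.** Change the SAP text and leave data collection alone.

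1. Keep the mixed model and state that saline is a level of delivery condition. Replace the four doses with saline, 5 min and 2.5 min, and menthol preference with cigarette assignment.
2. Pre-specify 1-df contrasts:
   - **(a1)** menthol versus non-menthol for nicotine averaged over both rates, as the main test of Hypothesis #1, reported with **(a2)** the same contrast relative to saline;
   - **(b)** 2.5 versus 5 minutes, as the only test of delivery rate, adjusted for nicotine infusion position;
   - **(c)** assignment by (b), two-sided with its confidence interval, as the only test of changed rate sensitivity.
3. Report nicotine versus saline separately. Note that saline always follows a nicotine infusion. The stated rationale, "This infusion order was chosen to minimize carry over effects between nicotine infusions", does not cover carry-over into saline, which could affect (a2).
4. State how the 0.025 level is allocated across outcomes, and label (b) and (c) secondary to (a1). Apply the same contrasts to the BQSU within its time-factor model at stated time points.
5. Limit the Hypothesis #1 conclusion to a larger response at a given rate, unless a shared-curve shift model is pre-specified and labelled assumption-dependent. Label log-linear, sigmoidal and AIC work exploratory.

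**Cost.** The confirmatory curve-shape claim is given up. Detectable differences are (2.241 + 0.842) × SE at 80% power and two-sided 0.025, assuming one infusion at each rate per session, for residual SD 10 / 20 mm:
- (c), SE = SD√(4/n): 11.3 / 22.5 mm at n=30, or 10.0 / 20.0 mm at the 38 completers in 8: Recruitment.
- (a2), SE = SD√(3/n): 9.7 / 19.5 mm at n=30.
- (a1) and (b), SE = SD√(1/n): 5.6 / 11.3 mm at n=30, if there is no condition-within-subject variance. With a condition SD equal to the residual SD, the affected contrast rises to 9.7 / 19.5 mm: (a1) if condition means cigarette condition, (b) if it means delivery condition.

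Three side clarifications can be made in the same edit but are not part of this point: which condition the random effect refers to, the four infusion conditions named for the Multiple-Choice Procedure, and the Background phrase "systematically examining the impact of nicotine delivery rate in both menthol and non-menthol smokers".

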*Saline infusions will follow each nicotine infusion to maintain a 10-min total infusion time for each test session. Abbreviations: CO: Alveolar carbon monoxide; HR/BP: Heart rate/Blood pressure; M-NWSC: Minnesota Nicotine Withdrawal Symptom Checklist; BQSU: Brief Questionnaire of Smoking Urges; CPT: Continuous Performance Test; DEQ: Drug Effects Questionnaire; SAFTEE: Systematic Assessment for Treatment Emergent Events. MCP: Money choice procedure.

7) Statistical analysis and sample size estimates

Specific Aim #1: To examine if switching from menthol to non-menthol cigarettes will change the dose-effect curves for positive subjective effects and alleviation of smoking urges as a function of nicotine delivery rate.

Positive subjective effects of nicotine will be assessed with the “Like the Drug Effects” and “Good Drug Effects” items from the DEQ, consistent with the FDA Guidance on abuse potential assessment (10). These items have been shown to correlate with the abuse potential of drugs of abuse. Effects will be tested using linear mixed effects models with peak change on each DEQ item as a response variable, cigarette-assignment (menthol vs. non-menthol), phase (1 vs.2) and nicotine delivery condition as within-subject factors and their interaction. Random effects for subject and condition within subject will be used to account for correlations between

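### The primary smoking-urge model names 60- and 120-minute readings that the session schedule does not supply; its time levels should be corrected before analysis

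*Combined protocol and SAP*

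**What the plan says.** Hypothesis #1 (section 4) is that switching to non-menthol cigarettes "will enhance responses to nicotine for both positive subjective effects and alleviation of smoking urges". For urges, section 7) Statistical analysis and sample size estimates, Specific Aim #1, takes over the mixed model used for subjective effects, with cigarette assignment, phase and nicotine delivery condition within subject, and adds: "we will also include time as a within-subject factor with outcomes for minute 0, 10, 30, 60 and 120". It does not say whether those minutes run from the start of the session or of each infusion.

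The documents describe the session in two ways.

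- **Three infusions.** B) Drugs states "In each test session, there will be a total of 3 infusions" and "Each infusion duration will be 10 minutes long". The Overview of the study agrees on the number ("Each session will include 3 infusions in the following order"), although it gives nicotine over 2.5 or 5 minutes and ten minutes only for saline. Table 2 starts infusions at minutes 0, 60 and 120, ends each ten minutes later, and ends the session at minute 180.
- **Apparently one infusion.** The Test Session text says "Participants will then receive the assigned infusion over a period of ten minutes" and then "Psychometric assessments and blood sampling will then continue for the next 120 minutes". The Table 2 footnote says "Saline infusions will follow each nicotine infusion to maintain a 10-min total infusion time for each test session".

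For subjective effects, the response is peak change on each Drug Effects Questionnaire (DEQ) item. No reference reading is named.

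**The concern.** The time levels of a primary model are fixed in the text but do not match the visit schedule. Minutes 60 and 120 of Table 2 carry only the starts of infusions 2 and 3. The readings that Table 2 does take at +45 min after each infusion are not among the model's levels.

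If nothing is changed, someone must decide after data collection which times enter the urge model and from which clock they run. The cigarette condition is open label, so that choice is better made beforehand. The same applies, with less force, to the DEQ reference. The two outcomes are the two domains of Hypothesis #1.

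**Working it through.** **Inputs.** Table 2 lists the BQSU at Baseline, 10, 30, 45, 70, 90, 105, 130, 150, 165 and 180. Infusions start at 0, 60 and 120. Baseline is taken as minute 0.

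**Clock restarted at each infusion** (the more natural reading, since delivery condition is already a within-subject factor). Required session minute = infusion start + model time.

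| Infusion (start) | 0 | +10 | +30 | +60 | +120 |
|---|---|---|---|---|---|
| 1, nicotine (0) | Baseline | 10 | 30 | 60: none | 120: none |
| 2, saline (60) | 60: none (last is 45) | 70 | 90 | 120: none | 180, but 60 min after infusion 3 starts |
| 3, nicotine (120) | 120: none (last is 105) | 130 | 150 | 180 | 240: session is over |

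Clean cells: 3 + 2 + 3 = 8 of 15. Accepting minutes 45 and 105 as the pre-infusion values gives 8 + 2 = 10 of 15. The 5 remaining failures are +60 for infusions 1 and 2 and +120 for all three.

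**Session clock.** Of 0, 10, 30, 60 and 120, only Baseline, 10 and 30 exist: 3 of 5, all from infusion 1. If minutes 45 and 105 stand in for 60 and 120, all five levels can be filled. Every one of them still precedes infusion 3, so the session's second nicotine infusion contributes nothing.

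**Levels that Table 2 does supply.** Pre-infusion, +10 and +30 are Baseline, 10, 30; 45, 70, 90; and 105, 130, 150. That is 9 of 9, with no reading used twice. Minutes 45 and 105 are each 15 minutes before the next start (60 − 45 and 120 − 105).

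**Infusion time.** 3 × 10 = 30 minutes per session, against the footnote's 10.

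**Secondary checks, same method.**

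- *DEQ.* There are 12 + 12 + 13 = 37 readings after the three starts. The first is at minute 1, and Table 2 lists none before infusion 1. Over +1 to +45 min there are 12 per infusion.
- *Withdrawal scale (MNWS) and Continuous Performance Test (CPT).* The plan wants 0, 30, 60 and 120 min, so 4 × 3 = 12 cells. MNWS has 2 + 1 + 2 = 5 clean, and CPT has 2 + 1 + 1 = 4. With minutes 45 and 105 as pre-infusion values these become 7 and 6. Neither has +60 or +120 for infusion 1, nor cleanly for saline.
- *Nicotine AUC.* The plan wants nine concentrations over 120 minutes. Table 2 has 1 + 7 + 7 + 7 + 1 = 23 samples (Baseline, seven per infusion to +45, minute 180). Its 120-minute windows hold 14 or 15.
- *Multiple-Choice Procedure (MCP).* It is rated at minutes 30 and 180, which is +30 after the first nicotine infusion and 180 − 120 = +60 after the second. A) Measures counts six test sessions, while Table 1 gives one per phase, so two. If six means infusions, 3 × 2 = 6 agrees, but Table 2 then gives only 2 × 2 = 4 ratings.

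**The case against.** The strongest reply is that this is a slip in a list of times. A linear mixed model uses whatever rows exist, and +10 and +30 are scheduled for all three infusions, so the effects of cigarette assignment and delivery rate remain estimable. This stands. A reader might infer that the urge model cannot be fitted at all, or that the primary urge data are missing. The documents support neither.

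A reader might also infer that +60 cannot compare the two nicotine rates. That goes too far: infusion 3 may be either rate, so across participants +60 can hold both. What remains is that +60 never includes saline and always belongs to the last infusion. A mixed model also cannot estimate a 120-minute level that has no clean reading; that gap is structural, not sporadic.

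On the DEQ, it is fair to say that the baseline self-report assessments in the Test Session text may include it, and that readings exist before infusions 2 and 3 (minutes 45 and 105). The missing reference is therefore mainly a clarification. It is not evidence that no baseline DEQ is taken, nor a reason to abandon peak change.

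Two further inferences should be resisted. Nine nicotine samples can be assembled for infusion 3 (minute 105, seven to minute 165, and minute 180), but they span 180 − 105 = 75 minutes, not 120. The absence of an MCP rating after saline is a conflict only if saline is one of the four infusion conditions in Exploratory Aim #1; that phrase can also mean two rates by two cigarette conditions.

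**Conclusion.** The urge time levels are wrong as written and should be corrected before analysis. Counted from each infusion, 8 of 15 cells are clean (10 of 15 with minutes 45 and 105); on the session clock, 3 of 5 times exist. The consequence is bounded: one empty level, one level tied to infusion position, and scheduled +45 readings left out, while the main contrasts survive on +10 and +30.

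This rests on Table 2 as printed, with its Baseline row taken as minute 0. The analysis times and the Test Session text fit a one-infusion session, which suggests text carried over from another design, but that is an inference.

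The DEQ reference is a clarification. The MNWS, CPT, AUC and MCP points concern exploratory aims and do not carry the same weight.

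**What to change.** Reconcile the MCP text in A) Measures, the Test Session text, the Table 2 footnote and the analysis section with Table 2, and state that analysis times run from the start of each infusion. If the three-infusion schedule stands:

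- **Urges (primary).** Use three levels: 0 (the last BQSU before each infusion: Baseline, minute 45, minute 105), +10 and +30. Keeping level 0 means that alleviation is still what is measured. State that minutes 45 and 105 follow an earlier infusion. Add +45 as a sensitivity analysis, noting that minutes 45 and 105 then serve twice.
- **DEQ (primary).** Keep peak change, and name one reference before analysis, applied identically to every infusion, session and phase. The last reading before each infusion qualifies only if a DEQ was taken at baseline. Add raw peak over +1 to +45 min as a sensitivity analysis.
- **MNWS and CPT.** Use +30 and +45, which Table 2 schedules for every infusion.
- **AUC.** Define the window and sample count from Table 2, and account for nicotine remaining from earlier infusions.
- **MCP.** Either rate it at the same delay after each nicotine infusion, or adjust for infusion position. Delay and position coincide in Table 2, so adjustment removes both together and cannot separate them. Say what the count of six means.

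Cost: rewording and a little more analysis, with no new urge readings. Aligning the MCP, if chosen, changes when that form is given. A shorter AUC window moves further from the total-dose meaning that the Biomarkers text gives it.
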